7.4 Storage

All study drugs should be kept in a secure place under appropriate storage conditions. The IP label on the bottle specifies the appropriate storage.

<<(JP) *Replace the second sentence of the paragraph above with:* A description of the appropriate storage conditions is specified in the document explaining the reconstitution procedures and other handling procedures for the investigational products.>>(End JP)

7.5 Compliance

The administration of all study drugs (including investigational products) should be recorded in the appropriate sections of the CRF.

Each time study drug is dispensed, compliance will be reinforced. When study drug is returned, compliance will be assessed based on returned tablet counts. Tablet counts will be recorded in the eCRF. Patients should demonstrate good compliance with the administration of study drug ($\geq 70\%$ and $\leq 130\%$) during the lead-in period. For patients with compliance between $\geq 70\%$ and $< 80\%$ or $> 120\%$ and $\leq 130\%$, the Investigator should ensure that there are

no systematic factors which may result in unacceptable compliance with study drug during the treatment period of the study. Such cases should be discussed with the study physician prior to randomization. During double-blind treatment period, patients judged to be non-compliant (defined as taking less than 80% or more than 120% of the prescribed dose of study drug) may continue in the study, but should be counselled on the importance of taking their study medication and applicable concomitant medications as prescribed.

7.6 Accountability

The study drug provided for this study will be used only as directed in the study protocol. The study personnel will account for all study drugs dispensed to and returned from the patient.

The investigator is responsible for making sure:

- That the IP is handled and stored safely and properly.
- That the IP is only dispensed to study patients in accordance with this protocol.

Patients should return all unused IP and empty containers to the investigator.

At the termination of the Clinical Study or at the request of AstraZeneca, the investigator will either return any unused IP to AstraZeneca or its designate, or destroy IP at the site depending on local regulations. If the IP is destroyed at site, the site personnel will account for all unused IP and for appropriate destruction. If the IP is returned to AstraZeneca or its designate, the study site personnel or the AstraZeneca monitor will account for all received IP received at the site, unused IP and for appropriate destruction. Certificates of delivery, destruction and return should be signed and archived.

<< **(JP)** Replace content in this section with: Study drug will not be distributed to the study site until the contract is concluded between the study site and AstraZeneca. The Investigational Product Storage Manager is responsible for managing the study drug from receipt by the study site until the return of all unused study drug to AstraZeneca. AstraZeneca will provide the study documents ‘Procedures for drug accountability’ and ‘Procedures for drug storage’ which describes the specific requirements. The Investigator(s) is responsible for ensuring that the subject has returned all unused study drug.>> **(End JP)**

7.7 Concomitant and other treatments

Changes in concomitant medication should be avoided during study participation, with the exception of situations defined in this protocol, but medication, which is considered necessary for the patient’s safety and well-being, may be given at the discretion of the investigators, who must decide if the patient should remain in study or need to be dismissed from study due to patient’s safety or interference with study objectives.

The administration of all medication must be recorded in the appropriate sections of the electronic CRF. The specific type of medication (trade or generic name), the indication for use, dosages, and the dates of usage should be reported.

After having completed or discontinued the study, patients will receive usual care and antidiabetic agents according to the investigator's judgment and according to local medical practice.

Restricted Medication/Class of drug:	Usage:
Metformin	A metformin dose which is outside the specified dose range for renal impairment (eGFR 25-75mL/minute/1.73m ²) according to local guidelines and/or investigator's judgement is not allowed.
Teriparatide, bisphosphonates and/or calcitonin	Treatment with teriparatide, bisphosphonates and/or calcitonin are allowed provided the dose has not changed within 30 days prior to enrolment.
Anemia treatment	Use of erythropoiesis stimulating agents including, but not limited to, erythropoietin epoetin alfa, epoetin beta, darbepoetin alfa, or methoxy-polyethylene-glycol-epoetin beta, are allowed provided the treatment has been ongoing for at least 6 months and the dose is unchanged from 3 months prior to Visit 1 and throughout the study.

Prohibited Medication/Class of drug:	Usage:
Antiviral drugs	Treatment for HIV and/or use of antiviral drugs (delavirdine, indinavir, nelfinavir, ritonavir, saquinavir) is not allowed.
Glucocorticoids (long term treatment)	Long term treatment with glucocorticoids (equivalent to oral prednisolone ≥ 10 mg (betamethasone ≥ 1.2 mg, dexamethasone ≥ 1.5 mg, hydrocortisone ≥ 40 mg) is not allowed, (two temporary periods of no longer than 10 days each are allowed during the study); topical or inhaled corticosteroids are allowed.

Weight loss medication	Use of weight loss medication, including but not limited to sibutramine, phentermine, orlistat, rimonabant, benzphetamine, diethylpropion, methamphetamine, Victoza (liraglutide) indicated for anti-obesity treatment, and/or phendimetrazine from 30 days prior to Visit 1 to end of study is not allowed.
------------------------	--

Guidelines with regard to standard of care and other therapy

During the duration of the study period, standard of care for each patient should be kept unchanged to the largest extent as possible, according to the judgment of the Investigator. Specifically, the dose of OADs, insulin, anti-hypertensive drugs, lipid lowering drugs and anti-platelet drugs should be kept constant throughout the entire study from start of run-in to end of follow-up (week 27).

However, in case of hypotension, the dose of any anti-hypertensive medication can be reduced according to the Investigator's judgement.

7.7.1 Other concomitant treatment

Other medication other than that described above, which is considered necessary for the patient's safety and well-being, may be given at the discretion of the Investigator and recorded in the appropriate sections of the CRF.

7.8 Post Study Access to Study Treatment---Not Applicable

8. STATISTICAL ANALYSES BY ASTRAZENECA

8.1 Statistical considerations

Multiplicity due to the two active treatment groups will be controlled by a Bonferroni adjustment, such that statistical significance will be determined according to a two-sided alpha level of 0.025. Within the saxagliptin 2.5 mg + dapagliflozin 10 mg treatment group the control of the alpha level in the testing of both co-primary endpoints (the percent change in urine albumin-to creatinine ratio (UACR) from baseline to 24 weeks and the change in HbA1c from baseline to 24 weeks) will require that each achieves statistical significance at the 0.025 level for a claim of superiority to placebo, and to proceed to a sequential comparison of secondary endpoints. Within the dapagliflozin 10 mg treatment group the control of the alpha level for the primary endpoint (the percent change in urine albumin-to creatinine ratio (UACR) from baseline to 24 weeks) will require the achievement of statistical significance at the 0.025 level for a claim of superiority to placebo, and to proceed to a sequential comparison of secondary endpoints. Parallel sequential testing strategies will be used for comparing each active treatment group to placebo for the secondary endpoints.

8.2 Sample size estimate

With 142 subjects per treatment group with post-baseline measurements, there is 90% power to detect a difference of 0.42% in mean change from baseline in HbA1c between saxagliptin/dapagliflozin treatment group and placebo and, separately dapagliflozin treatment group and placebo at significance level of 0.025, using a two sided alpha and assuming a standard deviation (SD) of 1.0%. Assuming 5% of the subjects do not have a post-baseline assessment, a total of 450 subjects (150 subjects per treatment group) need to be randomized. The estimated sample size of 142 subjects per group will also yield 92% power to detect a 35% difference in UACR for each comparison at an alpha level of 0.025, assuming a SD = 80%. Based upon existing pooled data for dapagliflozin in treating patients with eGFR <60 ml/min/1.73 m² on ACEi/ARB the minimal detectable difference for this study is 0.27% for HbA1c and 21% for UACR

The significance level used to infer statistical significance for comparisons of primary and secondary endpoints will be 0.025, representing a two sided alpha level. Within the saxagliptin 2.5 mg + dapagliflozin 10 mg treatment group the control of the alpha level in the testing of both co-primary endpoints (the percent change in urine albumin-to creatinine ratio (UACR) from baseline to 24 weeks and the change in HbA1c from baseline to 24 weeks) will require that each achieves statistical significance at the 0.025 level for a claim of superiority to placebo, and to proceed to a sequential comparison of secondary endpoints. Within the dapagliflozin 10 mg treatment group the control of the alpha level for the primary endpoint (the percent change in urine albumin-to creatinine ratio (UACR) from baseline to 24 weeks) will require the achievement of statistical significance at the 0.025 level for a claim of superiority to placebo, and to proceed to a sequential comparison of secondary endpoints. Parallel sequential testing strategies will be used for comparing each active treatment group to placebo for the secondary endpoints. In all analyses p-values will be represent two-sided tests, and will not be adjusted for multiplicity.

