The combination of DPP-4 and SGLT2 inhibition has therefore been proposed as a promising future option for T2DM patients with CKD (Scherthaner et al 2014).

Rationale for study design, doses and control groups

This study will be performed as part of the clinical development program for dapagliflozin for treatment of T2DM. This study intends to evaluate the efficacy, safety and pharmacodynamics of dapagliflozin and dapagliflozin in combination with saxagliptin in CKD patients with type 2 diabetes mellitus and albuminuria treated with ACEi or ARB who have inadequate glycemic control, defined as HbA1c $\geq 7.0\%$ and $\leq 11.0\%$, and renal impairment (eGFR ≥ 25 to ≤ 75 ml/min/1.73 m²).

The pharmacodynamic effects of saxagliptin and dapagliflozin have previously been studied in patients with renal impairment. Saxagliptin 2.5mg once daily significantly reduced UACR and HbA1c (Mosenzon et al 2014, Nowicki et al 2011, Kohan et al 2014) and dapagliflozin reduced UACR and HbA1c albeit the effect on HbA1c was not statistically different from placebo (Kohan et al 2014). All these doses were well-tolerated in this population and the saxagliptin dose of 2.5 mg is currently in the approved label for treatment of subjects with moderate or severe renal impairment. Dapagliflozin 10mg once daily was chosen because the

overall safety has not been different from 5mg once daily and the long term albuminuria lowering effects are thought to be more robust. Because the anti-glycemic effect of dapagliflozin wanes with decreasing GFR, HbA1c is the primary endpoint in the dapagliflozin + saxagliptin arm and secondary in the dapagliflozin arm.

Patients will be randomized to 24 weeks treatment with dapagliflozin 10 mg, dapagliflozin 10 mg plus saxagliptin 2.5 mg or matching placebo. The study will be an international multi-centre study at approximately 100 centres in North America, EU & ROW. It is planned to randomize a total of 450 patients (150 patients per treatment arm). The study is powered to detect a difference of 0.42% in mean HbA1c and 35% difference in UACR between active treatment and placebo following 24 weeks of treatment.

Dapagliflozin 10 mg once daily, saxagliptin 2.5 mg once daily or matching placebo will be added to usual care of patients who have inadequate glycemic control on their existing therapies.

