8.6.1 Analysis of the primary variable (s)

The analysis of the change in HbA1C from baseline to Week 24 will be based on a repeated measures model (RMM) including all scheduled time points following randomization up to and including week 24. The analysis of percent change from baseline in UACR from baseline to Week 24 will be conducted on the log-transformed UACR values using RMM. Separate RMM models will be used to compare saxagliptin/dapagliflozin with placebo, and to compare dapagliflozin 10 mg alone with placebo. RMM represent a longitudinal repeated measures analysis using ‘direct likelihood’, and include patients in the Full Analysis Set who have a baseline measurement and at least one post-baseline measurement. Analyses on HbA1c will only include measurements prior to the administration of rescue medication. Measurements made following rescue administration will not be included in HbA1c analysis.

The SAS procedure PROC MIXED will be used for primary analyses. The primary analysis models will each include the fixed categorical effects of treatment, week, randomization

stratification factor (i.e. anti-diabetic treatment strata) and treatment-by-week interaction as well as the continuous fixed covariates of baseline measurement and baseline measurement-by-week interaction. (In UACR analyses the natural logarithmic transformation will be applied to baseline UACR values prior to analysis.) An unstructured matrix for the within-patient error variance-covariance will be used. The denominator degrees of freedom will be calculated according to the Kenward-Roger method. A number of back-up models will be defined in the statistical analysis plan in case of non-convergence of the preferred model or other issues.

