Point estimates and 95% confidence intervals for the mean change in HbA1c within each model for each treatment group as well as the difference in mean change between the saxagliptin/dapagliflozin treatment group and placebo will be calculated. P-value of the differences in Week 24 estimates between saxagliptin/ dapagliflozin and placebo will be calculated. For UACR, point estimates and 95% confidence intervals for the mean percent change in UACR within each treatment group will be obtained by exponentiation of model estimates, and differences in mean percent change will be similarly calculated. P-values of the differences in Week 24 percent change estimates between each treatment group (saxagliptin/dapagliflozin and, separately, dapagliflozin 10 mg only) and placebo from each model will be calculated.

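### Do the unnamed UACR scale, the missing joint power and the undefined minimal detectable difference in section 8.2 call for a change to the sample size text?

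*Protocol*

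**What the plan says.** Section 8.2 sizes the trial on HbA1c: "With 142 subjects per treatment group with post-baseline measurements, there is 90% power to detect a difference of 0.42% in mean change", with an SD of 1.0%. It then applies the same number to UACR: "The estimated sample size of 142 subjects per group will also yield 92% power to detect a 35% difference in UACR for each comparison", with an SD of 80%. Section 1.1 repeats the two effects: "The study is powered to detect a difference of 0.42% in mean HbA1c and 35% difference in UACR between active treatment and placebo". None of these places says whether 35% and 80% are raw percent changes, log units, or a ratio with a coefficient of variation.

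The analysis is on the log scale. Under section 8.6.1 the UACR comparison "will be conducted on the log-transformed UACR values using RMM", and percent changes "will be obtained by exponentiation of model estimates, and differences in mean percent change will be similarly calculated".

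Section 8.1 divides alpha between the two active arms: "statistical significance will be determined according to a two-sided alpha level of 0.025". For the two co-primaries of the combination arm, the rule "will require that each achieves statistical significance at the 0.025 level for a claim of superiority to placebo".

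Section 8.2 also cites pooled dapagliflozin data in patients with reduced eGFR and adds that "the minimal detectable difference for this study is 0.27% for HbA1c and 21% for UACR".

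**The concern.** Three things look wrong at first.

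1. A test on ln(UACR) is powered by an active/placebo ratio and an SD of change in ln(UACR). Section 8.2 gives neither by name. Different readings of its two numbers imply different design effects, so the 92% might not describe the planned test. UACR is a primary endpoint for both active arms and the only one for dapagliflozin alone.
2. The combination arm can claim superiority only if HbA1c and UACR both succeed. The chance of that is lower than 90% and 92% taken singly, and it is not given.
3. The 0.27% and 21% follow directly after two statements of power at 90% or more. A reader could take them as effects the trial would reliably find, when they may be only the smallest observed differences that reach significance.

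At stake would be an underpowered UACR comparison, an overstated chance of success for the combination arm, or a misreading of what the trial can detect.

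**Working it through.** **Inputs.** From sections 8.1 and 8.2: n = 142 per group, two-sided alpha 0.025, HbA1c 0.42 with SD 1.0, UACR 35 with SD 80, 5% without a post-baseline value. Log SDs and correlations used below are assumptions; the protocol states none.

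**Method.** Two-sample noncentral t with 282 degrees of freedom and critical value 2.2534. The standard error factor is sqrt(2/142) = 0.1187, and the noncentrality is (difference/SD)/0.1187.

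**The protocol's own figures**

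- HbA1c: 0.42/0.1187 = 3.54; power 90.0% (stated 90%).
- UACR: (35/80)/0.1187 = 3.69; power 92.3% (stated 92%).
- Loss: 142/0.95 = 149.5, so 150 per group and 450 in total, as stated.
- Smallest significant observed difference: 2.2534 x 0.1187 x SD = 0.267 for SD 1.0 and 21.4 for SD 80 (stated 0.27% and 21%).

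**Readings of the UACR inputs**

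| Reading | Power | Effect as a reduction |
|---|---|---|
| 35/80, raw percent | 92.3% | 35 percentage points |
| 0.35/0.80, log units | 92.3% | 1 - exp(-0.35) = 29.5% |
| ratio 1.35, CV 80% (log SD sqrt(ln 1.64) = 0.703) | 91.0% | 1 - 1/1.35 = 25.9% |
| ratio 1.35, log SD 0.80 | 82% | 25.9% |
| ratio 0.65, log SD 0.703 | 99.8% | 35% |
| ratio 0.65, log SD 0.80 | 98.9% | 35% |
| ratio 0.65, log SD 1.0 | 91.5% | 35% |

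The log-unit reading also gives a threshold of 0.1187 x 2.2534 x 0.80 = 0.214, which is the stated 21% when written as 100 x ln. So one reading consistent with section 8.6.1 returns both UACR figures. The raw-percent reading returns them too, so the scale is unnamed, but a conflict with the planned test is not shown. The one reading in the table below 90% does not reproduce the stated 92%. For ratio 0.65, power drops below 90% only when the log SD exceeds 1.03.

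**Joint power, combination arm**

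- Stated inputs: 0.900 x 0.923 = 83.1% if independent; 84.1% at correlation 0.3; 85.0% at 0.5. Bounds are 0.900 + 0.923 - 1 = 82.3% and 90.0%.
- Ratio 0.65, independent: 0.900 x 0.998 = 89.8% at log SD 0.703; 0.900 x 0.989 = 89.0% at 0.80; 0.900 x 0.915 = 82.4% at 1.0.

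**Minimal detectable difference**

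- If the SDs are 1.0 and 80, power is 51% at a true 0.27 and 48% at 21.
- If the figures mean 90% power, the standardised effect is 0.420, so the pooled SDs would be 0.27/0.420 = 0.64 and 21/0.420 = 50. The text attributes the figures to pooled data whose SDs it does not give, so this cannot be ruled out.

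**The case for a change.** The best case for a change is that section 8.2 chose to state a UACR power and should state it in the units of the test. A clinician would read 35% as a reduction, and at either natural translation of an 80% SD that does not give 92%. The only success the combination arm can claim has a power nearer 83% than 90% on the stated inputs. The 0.27% and 21% match the significance thresholds so closely that a meaning of about 50% power is likely. A recalculation and three sentences would settle all three points.

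Part of this stands: the scale is not named, and the term minimal detectable difference is not defined. The rest carries less weight.

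- The mismatch for a 35% reduction runs in the safe direction, since power exceeds the stated figure unless the log SD is above about 1.0.
- Section 8.2 gives its powers separately for each endpoint and each comparison, and the rule that both co-primaries must succeed is written out in sections 8.1 and 8.2. Leaving out a joint figure is not a wrong statement, and any such figure needs a correlation that the protocol does not have.
- Adding 83% would build on the same UACR inputs that the first point wants replaced. With ratio 0.65 and a log SD of 0.70 to 0.80, joint power is 89% to 90%, close to the HbA1c power alone.
- The claim that an effect of 0.27% or 21% would be missed half the time depends on an assumption about SDs that the text attributes to another source.

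**Conclusion.** No change is needed. Every sample size and power figure in section 8.2 reproduces, and no underpowering for UACR is shown. HbA1c fixes the number of patients, so restating the UACR inputs cannot alter it. The log-scale test, the 0.025 level, the both-must-succeed rule and the sequential testing are set elsewhere in the protocol and use none of the disputed figures. A trial run as written would have the same data, tests and conclusions.

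What remains is wording: an unnamed scale, which an analyst can read as log units in line with section 8.6.1, and a label that a careful reader can check in one line. This rests on log SDs of about 0.70 to 1.0 being plausible for change in UACR, which the protocol does not document. With a log SD above 1.03, a 35% reduction would have less than 90% power, but naming the scale would not change that either. If a joint power is ever quoted, it should come from log-scale inputs over a range of correlations, not from the present 90% and 92%.

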8.3 Other statistical considerations

If superiority of is demonstrated within the saxagliptin 2.5 mg + dapagliflozin 10 mg treatment group the for each of the two primary endpoints (HbA1c and percent change from baseline UACR) at the 0.025 level and/or within the dapagliflozin 10 mg treatment group the for the primary endpoints (percent change from baseline UACR) at the 0.025 level then secondary endpoints will be compared separately between that treatment group and placebo at an alpha level of 0.025. Comparisons of secondary endpoints will be performed sequentially in the order prescribed in Section 2.2, and will cease for a given treatment group at the first instance a secondary endpoint dose not statistical significance in a secondary endpoint, or at the last comparisons, whichever occurs first. Superiority of a treatment to placebo will be inferred if statistical significance is demonstrated and greater improvement occurred with that treatment than placebo.

CCI

Continuous secondary and exploratory endpoints that are statistically compared and are measured at multiple instances during the 24 week double-blind treatment period will be evaluated using repeated measures models (RMM) which will include measurements from all scheduled time points following randomization up to and including week 24. Primary, secondary, exploratory, and eGFR safety parameters within or at the end of 24 weeks double-blind treatment analysed in the model will exclude all post-treatment results subsequent to glycemic rescue. However, the effect of exclusion on estimates and differences will be evaluated in sensitivity analyses. Continuous secondary and exploratory endpoints that are statistically compared and are only measured at baseline and at the end of the 24 week double-blind treatment period will be evaluated using analysis of variance models (ANOVA).

CCI

Analyses of secondary, safety, and exploratory categorical endpoints that represent proportions of subjects will be performed using a logistic regression model. The endpoints within or at the end of 24 weeks double-blind treatment analyzed in the model will exclude all post-treatment results subsequent to glycemic rescue. Details will be provided in the Statistical Analysis Plan.

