Urinalysis, dipstick		X	X	X	X	X	X	X	X	X		5.2.2
UACR, spot urine ^e	X		X	X	X	X	X	X	X	X		5.1.1
CGI			■	■	■	■	■	■	■	■		■
■			■	■	■	■	■	■	■	■		■
■			■	■	■	■	■	■	■	■		■
■			■	■	■	■	■	■	■	■		■
■			■	■	■	■	■	■	■	■		■
HbA1c	X		X	X	X	X	X	X	X	X		5.1.2
S-creatinine for eGFR calculation ^t	X	X	X	X	X	X	X	X	X	X		5.2.1
FPG		X	X	X	X	X	X	X	X	X		5.1.3
Assess FPG for Rescue			X	X	X	X	X	X	X	X		3.10.3
Fasting Serum Lipids (Total-C, LDL-C, HDL-C, TG, FFA)			X						X			5.1.12

Study period	Screening Period	Lead-in period	Randomization		Treatment period					Follow-up period	For details see Protocol Section				
			Fasting	3 ^{c,d,e}	Fasting	4 ^{c,d,e}	Fasting	5 ^{c,d,e}	Fasting			6 ^{c,d,e}	Fasting	7 ^{c,d,e}	Fasting
Visit number	1^a Non-fasting	2^{b,c} Fasting		3^{c,d,e} Fasting	4^{c,d,e} Fasting	5^{c,d,e} Fasting	6^{c,d,e} Fasting	7^{c,d,e} Fasting	8^{c,d,e} Fasting	9^{c,d,e} Fasting	10^{c,d} Fasting				
Week	-6	-4	0	1	4	8	12	16	24	27					
Day	-42 to -29	-28	1	8	29	57	85	113	169	190					
Visit window		±5	±0	±2	±5	±5	±5	±5	±5	±5	±3				

CCJ												
Parathyroid hormone (PTH)												
Hepatitis Screen Panel		X								X		5.2.2
												5.2.2

Assessment schedule footnotes

- a) Screening procedures, indicated under Visit 1, can be completed over multiple visits, provided all procedures have been completed, with the results reviewed, prior to Visit 2.
- b) Visit 3 should occur ≤ 42 days from visit 1 the period from visit 2 to visit 3 must be at least 28 ±5 days. Note: The single-blind Lead-in study medication and all the central laboratory results from Visit 1 must have been received at the site prior to completing the entry into Visit2.
- c) Central Laboratory samples must be collected in a fasting state (at least 8 hours fasting (drinking water is allowed) prior to the study visit) and subjects should be seen between 6 AM and 10 AM. Subjects must refrain from tobacco, caffeine for 12 hours, and alcohol for 24 hours prior to study visits. Ensure to collect all fasting blood samples prior to the morning dose(s) of blinded study medication. Doses of study medication on the day of the visits must be taken upon completion of study visit procedures.

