8.6 Methods for statistical analyses

Analyses on the variables shown below will only include measurements obtained prior to or on the date of rescue medication for some analyses. For other efficacy variables and exploratory variables, measurements after rescue medication will not be excluded from the analyses.

- Change from baseline in HbA1c (%)
- Change from baseline in FPG (mg/dL)
- Proportion of patients with HbA1c < 7%

C [Redacted]
C [Redacted]
I [Redacted]
[Redacted]
[Redacted]
[Redacted]

Further details will be specified in the Statistical Analysis Plan (SAP).

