8.6.2 Analysis of the secondary variable(s)

Comparisons of the secondary efficacy endpoints between dapagliflozin 10 mg and placebo will be performed only if the test for the primary UACR endpoint is significant. Secondary efficacy endpoints will only be compared between saxagliptin/dapagliflozin and placebo will only be performed if each comparison of both co-primary endpoints is significant. If statistical significance is achieved as prescribed above, then the secondary endpoints will be compared between that treatment (those treatments) and placebo in the order specified in Section 2.2. A sequential testing procedure will be employed for secondary comparisons in order to control the type I error rate at the 0.025 level. Statistical comparisons between each treatment and placebo will be only performed for a given secondary endpoint if all previous sequential tests for that comparison are also significant. Otherwise, the testing procedure will stop at the secondary endpoint that does not reach statistical significance.

The secondary endpoints percent change from baseline in total body weight at Week 24, change from baseline in FPG at Week 24, change from baseline in seated SBP at Week 24, and change from baseline in HbA1c at Week 24 (Dapagliflozin 10 mg) will be analyzed by RMM analyses, as described for the primary analyses.

The secondary analyses of proportions for subjects with at least a 30 percent reduction in UACR from baseline to Week 24 and, separately, proportions for subjects with an HbA1c of less than 7 percent at Week 24 will be analyzed using a logistic regression model with adjustment for randomization strata and baseline measurement.

C
C

[REDACTED]

I

[REDACTED]

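### Section 8.3 names ANOVA, with no baseline covariate, for continuous endpoints measured only at baseline and Week 24; ANCOVA would be more precise at no cost, visibly for exploratory measures only

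*Protocol*

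**What the plan says.** Section 8.3 chooses the model by how often an endpoint is measured. Continuous secondary and exploratory endpoints with several on-treatment visits go to a repeated measures model (RMM). Those that are statistically compared but "are only measured at baseline and at the end of the 24 week double-blind treatment period" go to a different method: they "will be evaluated using analysis of variance models (ANOVA". No model terms follow in the visible text.

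Baseline adjustment is written out elsewhere. Section 8.6.1 gives the primary RMM the "continuous fixed covariates of baseline measurement and baseline measurement-by-week interaction", together with the stratification factor. Section 8.6.2 says that percent change in weight and change in FPG, in seated SBP and (dapagliflozin arm) in HbA1c "will be analyzed by RMM analyses, as described for the primary analyses". The same section adjusts the logistic models for the two binary secondary endpoints for randomisation strata and baseline.

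Table 2 in section 4.2 shows a measurement with the two-point schedule: the row "Fasting Serum Lipids (Total-C, LDL-C, HDL-C, TG, FFA" is marked at Visit 3 (randomisation) and Visit 9 (Week 24) only.

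**The concern.** ANOVA and ANCOVA are different named models. Someone programming from 8.3 as worded would fit treatment, perhaps with stratum, and no baseline term. Someone fitting a baseline covariate would depart from the literal text. ANOVA is the only comparison method named for a continuous endpoint that has no baseline term visible anywhere in the protocol.

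Endpoints in this class have a baseline value by definition, so leaving it out as a covariate gives up precision for which the data are already collected. Section 8.3 also leaves open whether the response is the change or the Week 24 value, and under ANOVA the two give different treatment estimates. At stake are the width of the intervals for these comparisons and a choice between adjusted and unadjusted results that is better closed before unblinding.

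**Working it through.** **1. The plan's own figures.** The protocol gives no figure for the ANOVA endpoints. Its sample size calculation (section 8.2) reproduces, which confirms the alpha and group size used below. Inputs: difference 0.42%, SD 1.0%, two-sided alpha 0.025, power 90%.

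n per group = 2 × (2.2414 + 1.2816)² × 1.0² / 0.42² = 2 × 12.411 / 0.1764 = 140.7, so 141 against the stated 142. Power at 142 is 90.3% by the normal approximation and 90.0% by the noncentral t. Allowing for 5% without a post-baseline value, 142 / 0.95 = 149.5, so 150 as stated.

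**2. Which endpoints fall under the ANOVA sentence.**
- Weight, FPG, SBP and (dapagliflozin arm) HbA1c: several visits, RMM with baseline. Not affected.
- 30% UACR reduction and HbA1c below 7%: logistic regression with baseline. Not affected.
- Fasting lipids: Visits 3 and 9 only, and not a named primary or secondary endpoint. They fit the schedule condition. Whether they are statistically compared cannot be seen.

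**3. Gain in precision.** Assume equal variance s² at baseline and Week 24 and correlation rho. Per patient:
- ANOVA on change: variance 2s²(1 − rho)
- ANCOVA with baseline: variance s²(1 − rho²)
- Ratio: (1 − rho)(1 + rho) / [2(1 − rho)] = (1 + rho)/2

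The protocol does not give rho, so the table shows an assumed range. The third column is 142 divided by the ratio, rounded up. The fourth takes an effect that ANOVA on change would detect with 80% power at 142 per group, and gives the ANCOVA power as Φ[(2.2414 + 0.8416)/√ratio − 2.2414]. Using two-sided alpha 0.025 and 142 per group for an exploratory comparison is an assumption made for illustration.

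| rho (assumed) | variance ratio ANCOVA / ANOVA on change | n per group for ANOVA on change to match ANCOVA with 142 | ANCOVA power where ANOVA on change has 80% |
|---|---|---|---|
| 0.5 | 0.75 | 190 | 91% |
| 0.6 | 0.80 | 178 | 89% |
| 0.7 | 0.85 | 168 | 86% |
| 0.8 | 0.90 | 158 | 84% |
| 0.9 | 0.95 | 150 | 82% |

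**4. If the response is the Week 24 value.** The ANOVA variance is then s² and the ratio is 1 − rho²: 0.75, 0.64, 0.51, 0.36 and 0.19 over the same range. Under either response ANCOVA is no less precise in large samples.

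**The case against.** The strongest objection is that silence is not exclusion. Section 8.3 names three model families and lists terms for none of them. For the RMM and the logistic model the terms appear later, in 8.6.1 and 8.6.2. For the ANOVA they may stand in text that cannot be seen: a redacted block follows the sentence, and the exploratory outcomes (8.5.4) and exploratory analysis (8.6.5) are blacked out. Section 8.6 also says "Further details will be specified in the Statistical Analysis Plan (SAP". (The deferral in 8.3, "Details will be provided in the Statistical Analysis Plan", closes the paragraph on categorical endpoints, so it bears on this point less directly.)

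Much of this stands. A reader might infer that the plan analyses these endpoints without using the baseline value. The protocol does not say so: it lists no terms, and a change score already uses baseline by subtraction. For the same reason it is not shown that chance baseline imbalance goes uncorrected. With a change score, what remains is the regression of change on baseline. Nor can one say that every repeatedly measured endpoint is baseline-adjusted, because the covariates are visible only for primary and secondary endpoints. Waist circumference is a less secure example than lipids, since it is also taken at Visit 10 and so does not literally meet the only-twice condition.

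The objection does not remove the named method. Model terms can be left to the SAP, but 8.3 has already chosen a model label, and that label is not the usual one for a model with a continuous covariate.

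**Conclusion.** The point holds as a free improvement of narrow reach. Section 8.3 names ANOVA and no baseline covariate for a class of endpoints where baseline is always available, while the visible primary and secondary models adjust for it.

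A reader might take this as a loss of power for secondary endpoints, because the sentence in 8.3 covers secondary as well as exploratory endpoints. Section 8.6.2 rules that out: no named secondary endpoint falls under the ANOVA rule. The co-primary tests, the alpha control, the sequential secondary testing and the sample size are untouched.

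The size is a variance factor of (1 + rho)/2, or 0.75 to 0.95 for rho from 0.5 to 0.9. This rests on four assumptions: the response is change from baseline, the variances at the two time points are equal, rho lies in that range, and no baseline term is specified in the redacted text or the SAP. The gain is small if rho is high. Low priority.

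**What to change.** In section 8.3, replace the ANOVA label with analysis of covariance (ANCOVA), with treatment and randomisation stratum as factors and the baseline value as covariate. This brings the sentence into line with 8.6.1 and 8.6.2. It also settles the open response, because with baseline as a covariate the treatment difference is the same whether change or the Week 24 value is modelled.

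The cost is one wording change before unblinding, with no new data, visits or patients. If the SAP already specifies a baseline covariate for these endpoints, only the label in 8.3 needs aligning.
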